6.5 POOLING OF CENTRES

This section is not applicable because center/country is not included in the statistical model.

6.6 HANDLING OF MISSING DATA AND OUTLIERS

Every effort should be made to collect complete data at each visit for each patient. If not specified otherwise, missing data will not be imputed and remain missing. Potential outliers will be reported and analysed as observed.

Missing or incomplete AE dates are imputed according to BI standards (see "Handling of missing and incomplete AE dates") (3).

Missing data and outliers of PK data are handled according to BI standards. PK parameters that cannot be reasonably calculated based on the available drug concentration-time data will not be imputed.

6.7 BASELINE, TIME WINDOWS AND CALCULATED VISITS

Study days and visits will be labelled according to the CTP's flow chart.

Unless otherwise specified, baseline is defined as the time point closest to and prior to the first administration of study treatment. Note that for some study procedures (e.g. body weight, vital signs, laboratory tests), baseline may be the measurement made on the same day the study treatment was started. In such cases, these measurements will be assumed to have been taken according to the protocol, i.e. prior the first administration of BI 905711.

For laboratory parameters for which not only the examination date but also the sampling time was recorded, examination time should be taken into consideration when defining baseline. That is a laboratory measurement on the same date as the first administration of BI 905711 is considered as baseline if and only if the examination time of the laboratory measurement is before the first administration of BI 905711.

7. PLANNED ANALYSIS.

The following standards for End-Of-Text tables are defined:

- The set of summary statistics for continuous data is: N / Mean / Standard Deviation (StD) / Min / Median / Max. For tables that are provided for endpoints with some extreme data, median, quartiles, and percentiles should be preferred to mean, standard deviation, minimum, and maximum. If not otherwise specified, the abbreviation Pxx should be used for displaying the xxth percentile. Other than the Min and Max, all statistics will be presented to one more decimal place than the raw data.
- Tabulations of frequencies for categorical data will include all possible categories and will display the number of observations in a category as well as the percentage (%) relative to the respective treatment group (unless otherwise specified, all patients in the respective patient set whether they have non-missing values or not). The precision for percentages will be one decimal place. The category "missing" will be displayed only if there are actually missing values.
- For time-to-event analysis tables the set of statistics is: number of patients [N(%)], number of patients with event [N(%)], <time to event> [months] followed by 25th percentile (P25), median, 75th percentile (P75) and number of patients censored [N(%)]. If not specified otherwise the duration as well as the time to event will be displayed in months.

Where applicable, conversion from days to weeks, months, and years will be as follows:

- Weeks = days \div 7
- Months = $(days \times 12) \div 365.25$
- Years = days \div 365.25.

General aspects for PK

Descriptive data analysis of PK endpoints and concentrations will be performed according to BI procedures.

Plasma concentration data and parameters of a subject will be included in the statistical pharmacokinetic (PK) analyses if they are not flagged for exclusion due to a protocol deviation relevant to the evaluation of PK (to be decided no later than in the Report Planning Meeting) or due to PK non-evaluability (as revealed during data analysis, based on the criteria specified below). Exclusion of a subject's data will be documented in the CTR.

Important protocol deviations may be

- Incorrect trial medication taken, i.e. the subject received at least one dose of trial medication the subject was not assigned to
- Incorrect dose of trial medication taken
- Use of restricted medications

Plasma concentrations and/or parameters of a subject will be considered as non-evaluable, if for example.

• Missing samples/concentration data at important phases of PK disposition curve.

Plasma concentration data and parameters of a subject which are flagged for exclusion will be reported with its individual values but will not be included in the statistical analyses. Only concentration values within the validated concentration range and actual sampling times will be used for the calculation of pharmacokinetic parameters. Concentrations used in the pharmacokinetic calculations will be in the same format as in the bioanalytical report (that is to the same number of decimal places provided in the bioanalytical report).

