¹⁰Includes Hematology, Biochemistry, Coagulation, and Urine. Refer to protocol Section 5.2.3 for specific laboratory requirements. Safety lab tests performed during screening do not need to be repeated at Cycle 1 Day 1 if performed within 10 days prior to treatment start and there is no clinical reason to repeat lab tests. During Cycle 1, safety labs should be performed at Day 1, and Day 8. On Cycle 1 Day 1, patients also need to have safety labs performed between 4-6 hours post-dose and repeated at 24 hour timepoint. A patient that experiences an elevated ALT and/or AST value after Cycle 1 Day 1 administration needs to have safety labs performed post-dose after the second and third administrations to assess ALT and AST values. During subsequent cycles, safety labs should be performed within 48 hours prior to each treatment administration as well as at EOT, EOR and at Follow up for PD. Safety lab tests are to be repeated as clinically indicated. At Screening visit, patients are to be tested for hepatitis virus infection which includes hepatitis B surface (HBs) antigen, presence of HBc antibody together with HBV-DNA, and presence of hepatitis C RNA. Results for hepatitis virus infection obtained in routine diagnostics are acceptable if done within 14 days before the informed consent date.

Page 16 of 165

Proprietary confidential information © 2023 Boehringer Ingelheim International GmbH or one or more of its affiliated companies

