4.1.4 Drug assignment and administration of doses for each patient

The study drug will be prepared and handled according to the 'Preparation and Handling of BI 905711 for 1412-0001 instructions which will be filed in the ISF. Upon notification that a patient will be treated in the study, the pharmacy will prepare the study drug at the assigned dosage for administration to the patient.

The Cycle 1 Day 1 dose will be calculated using the Cycle 1 Day 1 weight or up to 3 days prior as the reference weight. If the patient's weight changes by $\leq 10\%$ compared to the reference weight, the dose (in mg) may remain the same for subsequent cycles. If the weight changes by $\geq 10\%$ the dose will be recalculated and the new weight will be used as the reference weight.

BI 905711 will be given as an intra-venous infusion by authorised site staff in a specialised unit where emergency care can be provided (e.g. intensive care unit available, medical personnel trained in advanced life support). Appropriate drugs and medical equipment to treat anaphylactic reactions must be immediately available, and study personnel must be trained to recognise and treat anaphylaxis. No routine premedication will be required for BI 905711 i.v. infusions.

Page 64 of 165

Proprietary confidential information © 2023 Boehringer Ingelheim International GmbH or one or more of its affiliated companies

The infusion should take place over 30 minutes (\pm -10 minutes), unless there is a necessity of administration rate reduction according to the protocol (e.g., in case of infusion-related reaction). If a patient's weight is \leq 50 kg, the infusion duration may be less than 30 minutes depending upon the infusion rate and the patient's condition.

Priming and flushing should not be included in the administration duration. Total storage time for ready-to-use solution at room temperature should not exceed 150 minutes between preparation and end of infusion time.

Post-infusion observation period for phase Ia and phase Ib:

- Patients will remain under surveillance for at least 8 hours after first, second and third administrations of BI 905711. During the post-infusion observation period, body temperature, pulse rate and blood pressure will be measured at the end of the infusion and every 2 hours (± 15 minutes) thereafter.

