7.5 HANDLING OF MISSING DATA

No imputation will be performed on missing efficacy data. Missing baseline laboratory values will be imputed by the respective values from the screening visit. No other imputations will be performed on missing data although every effort will be made to obtain complete information on all adverse events, with particular emphasis on potential DLTs.

Pharmacokinetcis:

Handling of missing PK data will be performed according to the relevant BI internal procedure.

PK parameters that cannot be reasonably calculated based on the available drug concentration-time data will not be imputed.

Page 102 of 165

Proprietary confidential information © 2023 Boehringer Ingelheim International GmbH or one or more of its affiliated companies

If the actual sampling time is not recorded or is missing for a certain time point, the planned time will generally be used for this time point instead. Pharmacokinetic parameters which cannot be determined will be identified by "not calculated" (NC).

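### SAP 6.7 presumes same-day Cycle 1 Day 1 measurements are pre-dose, so a post-infusion vital sign or an untimed post-dose lab can be taken as baseline

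*SAP*

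**What the plan says.** SAP 6.7 starts from a sound definition: "baseline is defined as the time point closest to and prior to the first administration of study treatment". It then notes that for some procedures, with body weight, vital signs and laboratory tests as examples, the baseline may be a measurement from the day treatment started, and adds: "In such cases, these measurements will be assumed to have been taken according to the protocol, i.e. prior the first administration of BI 905711".

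The next SAP paragraph makes an exception. Its scope is "For laboratory parameters for which not only the examination date but also the sampling time was recorded". Within that scope, a lab from the day of first dosing "is considered as baseline if and only if the examination time of the laboratory measurement is before the first administration of BI 905711". SAP 6.7 has no matching rule for vital signs, or for labs without a recorded time.

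The protocol's Cycle 1 Day 1 schedule reads as follows.

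- **Labs** (flow-chart footnote 9 for Phase Ia, footnote 10 for both Phase Ib charts): "On Cycle 1 Day 1, patients also need to have safety labs performed between 4-6 hours post-dose". The pre-dose set is waivable: "Safety lab tests performed during screening do not need to be repeated at Cycle 1 Day 1 if performed within 10 days" before treatment start, provided there is no clinical reason to repeat them.
- **Vital signs** (Protocol 4.1.4): for at least 8 hours after each of the first three administrations, "body temperature, pulse rate and blood pressure will be measured at the end of the infusion and every 2 hours".

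Protocol 7.5 covers the missing case: "Missing baseline laboratory values will be imputed by the respective values from the screening visit".

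**The concern.** The SAP justifies its presumption by appeal to the protocol, but the protocol deliberately schedules several Day 1 measurements after the dose. A programmer who follows SAP 6.7 literally, with only a date to work from, could take one of these as baseline.

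The early post-dose readings are there to show what the first dose does. The flow-chart footnotes, for example, make an ALT or AST rise after Cycle 1 Day 1 a trigger for further post-dose labs after the second and third administrations. If such a reading serves as the reference value, a first-dose change is measured against itself, and a later return to normal looks like improvement. For vital signs, a post-infusion temperature or blood pressure could be listed as the pre-treatment finding.

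**Working it through.** The plan gives no figure to reproduce. The check sets the SAP rule against the protocol schedule and follows the consequences through the planned outputs.

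**Step 1: count the scheduled post-dose records on Day 1.**

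- Vital signs: one set at end of infusion plus one every 2 h over 8 h, so 1 + 8/2 = 5 sets.
- Labs: 1 set, at 4-6 h. The 24 h repeat falls on Day 2 and is not a same-day record.

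**Step 2: apply SAP 6.7 to labs.** There are four cases.

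| Pre-dose Day 1 lab | Sampling time recorded | Result under SAP 6.7 |
|---|---|---|
| Drawn | Yes | Pre-dose value is baseline: correct |
| Waived | Yes | 4-6 h value is excluded and the screening value applies: correct, and consistent with Protocol 7.5 |
| Drawn | No | Two same-day values, both presumed pre-dose: SAP 6.7 does not say which to use |
| Waived | No | The 4-6 h value is the only same-day value and is presumed pre-dose: a post-dose baseline |

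In the last case the baseline does not count as missing, so the screening value in Protocol 7.5 is never reached.

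**Step 3: apply SAP 6.7 to vital signs.** No time rule applies. If all same-day records are presumed pre-dose, the closest-and-prior definition cannot rank a pre-infusion reading against the five later sets. The flow charts also allow the physical examination, which they describe as including vitals, to be skipped on Day 1 if done within 24 h. A true pre-dose set on that date is therefore not certain.

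**Step 4: follow an untimed, waived-pre-dose lab through SAP 7.8.2.** That section counts baseline labs as part of the on-treatment period, and Table 6.1:1 starts that period on the date of first administration. Take a purely hypothetical patient with grade 0 at screening, grade 3 at 4-6 h and grade 0 at the last value.

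| Output | Screening value as baseline | 4-6 h value as baseline |
|---|---|---|
| Worst on-treatment grade | 3 | 3 |
| Worst to last | 3 to 0 | 3 to 0 |
| Baseline to worst | 0 to 3 | 3 to 3 |
| Baseline to last | 0 to 0 | 3 to 0 |

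The numerical difference from baseline is distorted in the same way as the last two rows. The first two rows do not change.

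**Step 5: follow vital signs through SAP 7.8.3.** They are only listed, against findings before treatment. No change-from-baseline summary or shift table is planned.

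**Step 6: are clock times captured?** Protocol 5.3.2 says they are recorded in the CRF for dosing and PK sampling. No such statement was found for safety labs or vital signs. The SAP's own wording allows for labs without a time.

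**The case against.** The strongest reply is that the SAP already protects the main laboratory case. A timed 4-6 h sample cannot be baseline, even when the pre-dose set was waived. That stands, and it limits the laboratory part of this point to samples without a recorded time. A reader might infer that the scheduled post-dose labs generally become baseline; the documents do not support that.

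A reader might also infer that an acute grade 3 rise would drop out of the safety report. It would not. As step 4 shows, it stays in the worst on-treatment grade and the worst-to-last transition. Clinically relevant laboratory and vital-sign changes are also recorded as adverse events (Protocol 5.2.6.1.1). Infusion-related reactions and cytokine release syndrome within 72 hours of dosing are reported as events of special interest whatever their grade (Protocol 5.2.6.1.4).

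Nor do the Phase Ia results in Protocol 1.2 show the problem occurring. Three of the four drug-related grade 3 events were transient AST or ALT increases, but the text does not say when they arose, so nothing places them in a 4-6 h sample. They were also captured as adverse events.

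Two further replies stand only in part.

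- A sample scheduled after the dose does not fit naturally under a presumption that measurements were taken as the protocol directs. The intent is therefore clear, but the rule as written gives no means of separating pre-dose from post-dose records that carry only a date.
- The eCRF or the sponsor's laboratory data standard cited in SAP section 8 may supply clock times or time-point labels. That cannot be checked from these documents, and protocol silence does not show that times are missing.

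The flow charts with the Cycle 1 lab schedule are marked as no longer applicable under protocol version 7.0. The reduced schedule that replaces them starts at Cycle 6, so they still describe how Cycle 1 was run. Protocol 4.1.4 is current text.

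**Conclusion.** The point holds in limited form and is minor. SAP 6.7 states a presumption that conflicts with the protocol's Day 1 schedule, and its only safeguard covers timed labs. The exposure is vital signs and untimed labs.

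For an untimed lab, three outputs are affected: difference from baseline, baseline-to-worst transition and baseline-to-last transition. For vital signs, the effect is confined to one listing. No primary endpoint, and no count of patients with treatment-emergent adverse events, depends on this baseline.

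The number of patients affected is not stated. The sharpest laboratory case needs both a waived pre-dose set and a missing sampling time, so it could be none and may be small. The conclusion assumes that some Day 1 records carry neither a usable clock time nor a time-point label, and that the 4-6 h sample falls on the calendar date of dosing.

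**What to change.** Amend SAP 6.7 in three respects:

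1. Extend to vital signs the condition now confined to timed labs: a same-day value is baseline only if shown to precede the first administration, by clock time or by planned time-point label.
2. Exclude the Cycle 1 Day 1 4-6 h labs and all post-infusion vital signs from baseline selection, whether or not a clock time exists.
3. Where no confirmed pre-dose Day 1 value exists, use the last screening value. For labs this agrees with Protocol 7.5.

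The cost is a sentence or two in SAP 6.7 and a filter in the baseline derivation. No new data are needed.

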7.1 DEMOGRAPHIC AND OTHER BASELINE CHARACTERISTICS

Only descriptive statistics are planned for this section of the report.

7.2 CONCOMITANT DISEASES AND MEDICATION

Only descriptive statistics are planned for this section of the CTR.

Concomitant diseases will be coded using the most current version of Medical Dictionary for Regulatory Activities (MedDRA).

Concomitant medications will be coded using the most current version of World Health Organization Drug Dictionary (WHO DD). Concomitant medications will be classified according to the Anatomical Therapeutic Chemical (ATC) classification system. The third ATC level will be used to categorize concomitant therapies by therapy type. In situations where a medical product may be used for more than one equally important indication, there are often several classification alternatives. As appropriate, patients receiving concomitant medications with more than one possible ATC level 3 category will be counted more than once. Explanatory footnotes will clarify the possible double counting.

Separate summaries of concomitant medications started prior to and after first administration of trial medication will be produced.

7.3 TREATMENT COMPLIANCE

Only descriptive statistics on the treated set are planned for this section of the CTR. The actual dose versus the planned dose for infusion drug administration for each patient will be listed.

7.4 PRIMARY OBJECTIVE ANALYSIS

This trial will be performed as an open label.

7.4.1 Main Analysis

The primary analyses for Phase Ia:

In order to identify the MTD of the trial, the number of patients at each dose level that had DLT during the MTD evaluation period will be presented, excluding patients who discontinue during the first treatment cycle for reasons other than a DLT. The BLRM as described in Section 7.1 of the CTP will be analyzed using the number of patients at each dose that had DLTs during the MTD evaluation period among the patients in the MTD set. The prior defined in Table 7.1: 1 of the CTP will be used for the analysis. The resulting posterior distribution of the DLT rates of the doses tested during the trial will be summarized using their mean, SD, 2.5% quantile, median, and 97.5% quantile. Additionally, the posterior probabilities of the DLT rate lying in the intervals [0, 0.16) (under dosing), [0.16, 0.33) (target dosing), and [0.33, 1] (overdosing) will be computed and listed for each dose. The posterior probabilities of under dosing, target dosing, and overdosing of the tested dose levels will additionally be visualized in a bar diagram that further displays which of the dose levels satisfy the EWOC criterion.

In addition, the number of patients with DLTs that occurred during the entire treatment period will be summarized at each dose level.

The primary analyses for Phase Ib:

The primary endpoints in the dose-expansion part are objective response (OR) and PFS derived from the data of all cycles. The PFS will be summarized using PFS4 rate, defined as the proportion of patients with PFS >= 4 months, and will be presented descriptively together with 95% confidence intervals. Objective response will be analyzed in terms of objective response rate (ORR), defined as the proportion of patients with best overall response of complete response (CR) or partial response (PR). For each dose level, the proportion of patients with objective response (CR and PR) will be calculated with 95% confidence interval.

Kaplan-Meier estimates will be used to display the distribution of PFS for each treatment group on a Kaplan-Meier curve. To support the plot, estimated survival probabilities at specific time points of interest (scheduled imaging time points) will be tabulated along with 95% CIs using Greenwood's variance estimate. In addition, the Kaplan-Meier estimates will be used to provide estimates of the median, 25th, and 75th percentiles.

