2. TRIAL OBJECTIVES AND ENDPOINTS

2.1 MAIN OBJECTIVES, PRIMARY AND SECONDARY ENDPOINTS

2.1.1 Main objectives

Phase Ia:

- Explore safety and establish the maximum tolerated dose (MTD)/recommended dose levels for phase Ib expansion phase of BI 905711 based on the frequency of patients experiencing dose limiting toxicities (DLTs) during the MTD evaluation period. The MTD evaluation period is defined as the first two treatment cycles (from first dose administration until the day preceding the third dose administration or end of REP in case of discontinuation before start of Cycle 3).
- Explore pharmacokinetics/pharmacodynamics and efficacy to guide the determination of a potentially effective dose range for phase Ib in the absence of MTD.

Phase Ib:

• Evaluate efficacy and safety of BI 905711 at a potentially effective dose range and determine the Recommended Phase 2 Dose (RP2D)

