3.3.4.4 Replacement of patients for MTD determination and PK evaluation in phase Ia

Patients who experience a DLT during the MTD evaluation period were not replaced. The following patients without DLT during the MTD evaluation period were considered non-evaluable for MTD determination and were not included in the BLRM analysis:

- Patients who withdrew consent or who were lost from follow-up before completing first two cycles of study treatment.
- Patients who have received less than 70% of the planned BI 905711 doses during first two cycles of study treatment
- Patients who missed 2 or more partial or complete visits during the first two cycles of study treatment.
- Patients with missing PK and evaluation of safety parameters.

These patients were replaced for DLT evaluation during the MTD evaluation period if not decided otherwise by the SMC (e.g. if the number of evaluable patients for the current dose cohort is considered sufficient for a dose escalation decision or MTD determination).

Of note, the dose escalation was determined based on all the safety information of all treated patients including those who were not included in the BLRM analysis.

Page 59 of 165

Proprietary confidential information © 2023 Boehringer Ingelheim International GmbH or one or more of its affiliated companies

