6.3 SUBJECT SETS ANALYSED

- Screened set: This patient set includes all subjects who have signed the informed consent. The screened set will be used for patient disposition tables.
- Treated set (TS): This includes all subjects who were dispensed study medication and were documented to have been treated with at least one dose of BI 905711. This TS is used for both safety and efficacy analyses.
- MTD evaluation set (MTDS): This includes all patients in the TS who were not replaced for the MTD determination. The MTDS is used for the primary analyses of DLTs and MTD determination. Rules for replacement of patients are defined in the CTP Section 3.3.4.4. The list of replaced patients will be provided by the Trial

Clinical Monitor no later than the last RPM and should be documented in the RPM minutes.

• Pharmacokinetic parameter analysis set (PKS): This includes all subjects in the treated set (TS) who provide at least one PK endpoint and was not excluded due to a protocol deviation relevant to the evaluation of PK or due to PK non-evaluability (as specified in the following subsection Pharmacokinetics). Descriptive and potential model based analyses of PK parameters will be based on the PKS.

All analyses on immunogenicity will be based on Treated set (TS).

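### SAP 7.4.1 sets the population for the primary DLT table by first-cycle discontinuation alone, which conflicts with the two-cycle evaluation period and with the MTD evaluation set named in SAP 6.3

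*SAP*

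**What the plan says.** SAP 7.4.1 describes two outputs for Phase Ia in consecutive sentences. The first is the number of patients per dose level with a DLT in the MTD evaluation period, "excluding patients who discontinue during the first treatment cycle for reasons other than a DLT". The second is the Bayesian logistic regression model (BLRM), fitted "using the number of patients at each dose that had DLTs during the MTD evaluation period among the patients in the MTD set".

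The other relevant places use two cycles, or the MTDS, or both:

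- Protocol 2.1.1: "The MTD evaluation period is defined as the first two treatment cycles". For a patient who stops early, the window runs to a later end: "or end of REP in case of discontinuation before start of Cycle 3".
- SAP Table 6.1:1 ends the period at the second administration plus 35 days, database lock or the start of the third cycle, whichever comes first.
- Protocol 3.3.4.4 lists who is non-evaluable when no DLT occurred. The list includes "Patients who withdrew consent or who were lost from follow-up before completing first two cycles of study treatment" and "Patients who have received less than 70% of the planned BI 905711 doses during first two cycles of study treatment". It also names patients who missed two or more visits in those cycles and patients with missing PK and safety evaluation. Such patients stay out of the BLRM. A patient with a DLT in the period is not replaced.
- SAP 6.3: "The MTDS is used for the primary analyses of DLTs and MTD determination". Its definition reads: "This includes all patients in the TS who were not replaced for the MTD determination".
- Protocol 7.3 restricts MTD determination to DLT-evaluable patients.

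**The concern.** The number of patients with DLTs in the MTD evaluation period is a Phase Ia primary endpoint (protocol 2.1.2, SAP 5.1), and SAP 4 keeps the primary analyses in the abbreviated report. SAP 7.4.1 is the specific instruction for that table. A programmer who follows it produces a population tied to one cycle for an endpoint defined over two, next to a model fitted on a different set.

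The sentence asks for a count, but a denominator comes with it by default. The table standards in SAP 7 require categorical tabulations to show a percentage relative to the treatment group, and 7.4.1 makes no exception. When no DLTs are seen, the number of evaluable patients per dose is most of what the table tells the reader, so it should be the right number.

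**Working it through.** **1. What the 70% rule implies.** Phase Ia cycles last 14 days with one dose on Day 1 (Phase Ia flow chart), so two doses are planned in the window.

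- Stop in Cycle 1 after one full dose: 1/2 = 50%, below 70%, so non-evaluable if there is no DLT.
- Stop in Cycle 2 after two full doses: 2/2 = 100%, so the rule is met.
- Full first dose and a fraction x of the second: (1 + x)/2 < 0.70 when x < 0.40. This assumes the rule is applied to the amount given.

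**2. Patient types set against each rule.** The last column applies the 7.4.1 clause to the treated set.

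| Patient | Protocol 3.3.4.4 | SAP 6.3 (MTDS) | SAP 7.4.1 clause |
|---|---|---|---|
| A. Stops in Cycle 1, no DLT, replaced | out | out | out |
| B. Stops in Cycle 2 after both doses, followed to end of REP, no other criterion met, no DLT | in | in | in |
| C. Withdraws consent or is lost in Cycle 2, no DLT, replaced | out | out | **in** |
| D. Less than 70% of dose, two or more missed visits, or missing PK and safety, because of events in Cycle 2; no DLT, replaced | out | out | **in** |
| E. Stops in Cycle 1 for another reason, then has a DLT before end of REP | in, DLT counts | in | **out** |
| F. Non-evaluable in Cycle 2, no DLT, SMC decides not to replace | out | **in** | **in** |

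Rows C and D enlarge N. Row E removes an event. Row F is a separate gap in the MTDS definition. If the clause is instead applied on top of the MTDS, rows C and D fall out, but row E is still lost and the table still need not match the model's set.

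**3. Does it matter for the MTD?** The model is logit(p) = log(α) + β·log(d/3.6), with the three-component prior of protocol Table 7.1: 1. I refitted it by numerical integration.

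- Reproduction: for scenario 10 of Table 10.3: 1 (0.6 mg/kg, 2 DLTs in 4 patients) the probability of overdose is 0.215, against 0.210 in the protocol. All twelve scenarios checked agree within 0.02, and the prior interval probabilities of Table 7.1: 2 agree within 0.004.
- Reported data: protocol 1.2 gives 0 DLTs in 48 treated patients. Evaluable numbers per dose are not given, so I assumed per-dose counts totalling 48, 26, 25 and 20. The overdose probability at 4.8 mg/kg is then 0.0002, 0.0025, 0.0025 and 0.0058, against the limit of 0.25. The crude rate is 0/N = 0 for any N.
- Row F, hypothetical data only: take one patient without a DLT out of the last cohort (4 to 3). Scenario 10 moves from 0.215 to 0.289 and fails the limit. Scenario 15 moves from 0.157 to 0.214 and still passes. So the membership of the MTDS can matter when DLTs occur.

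**The case against.** The strongest reply is that the SAP already holds the answer. Section 6.3 names the MTDS for the primary DLT analyses and ties it to protocol 3.3.4.4, and the BLRM, which determines the MTD, runs on that set. The one-cycle clause also does much of the work of the 70% rule, since a Cycle 1 dropout has had only half the planned doses. And keeping or dropping patients without a DLT cannot change a count of patients with one. All of this stands. It confines the point to an internal contradiction about the table, but it does not remove the contradiction: 7.4.1 and 6.3 give different populations, and row E shows that the count itself can change.

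A reader might go further and infer that Cycle 2 discontinuations are wrongly treated as evaluable and that the DLT rate is therefore diluted. The documents do not support this.

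- A patient who stops in Cycle 2 has normally started both infusions, and the window extends to the end of the REP. With the second dose on Day 15, that is Day 45 to 50 (15 + 30 to 15 + 35). A patient who continues is covered to about Day 28. Such patients may well be evaluable (row B).
- The documents do not give the number of non-evaluable Cycle 2 discontinuations. The median treatment duration of 30.5 days does not supply it.
- With no DLTs reported there is no crude rate to dilute, and neither document plans a confidence interval for a DLT rate.

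**Conclusion.** The inconsistency is real. SAP 7.4.1 conflicts with SAP 6.3, with the two-cycle period in protocol 2.1.1 and SAP Table 6.1:1, and with the evaluability rules in protocol 3.3.4.4. Its possible effects are an N per dose that includes some non-evaluable patients, a missed REP event after a Cycle 1 stop, and a table that does not match the model's set. The number of patients involved cannot be derived from the documents.

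For this trial the effect on the MTD conclusion is nil. That rests on the protocol's report of 0 DLTs in 48 patients and, for the overdose probabilities, on the assumed per-dose counts, all of which leave 4.8 mg/kg far below the limit. What is at issue is the correctness of a primary-endpoint table and its agreement with the model beside it.

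**What to change.** Make three changes to the SAP text:

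1. In 7.4.1, delete "excluding patients who discontinue during the first treatment cycle for reasons other than a DLT".
2. State there that the DLT table and the BLRM both use the MTDS, and show N evaluable for each dose level.
3. In 6.3, define the MTDS as treated patients who are evaluable under protocol 3.3.4.4. This includes every patient with a DLT in the MTD evaluation period and leaves out every non-evaluable patient, whether or not the SMC chose to replace that patient.

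The cost is a few lines of text and a check of the evaluability list, which SAP 6.3 already routes through the report planning meeting. Denominators may be slightly smaller. No new data are needed.
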